6. OBJECTIVES

6.1 Primary objective

The primary objective and primary endpoint are shown in the table below:

Primary objective	Primary endpoint
The aim of this study is to perform a prospective randomized comparison of postoperative recovery between the 27G and larger gauge surgical approach. Patients will be randomized to be operated using 27 gauge or a larger	The outcome of the trial is to prospectively determine whether ultra- small gauge surgery (27G) improves postoperative outcome and patient morbidity.
gauge size.	 For this purpose, the following postoperative parameters will be used: Post-operative redness (Eye Photo) Ophthalmic examination including biomicroscopy to evaluate the amount of intra-ocular inflammation.

The secondary objective and secondary parameters are shown in the table below:

Secondary objective	Secondary endpoint
To obtain additional outcome parameters for both the 27 gauge and larger gauge surgery	Postoperative parameters: - Visual Acuity (LogMAR BCVA) - Intra-ocular pressure (mmHg) - Pain assessment (Questionnaire with visual analogue scale)

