To be completed by the patient about postoperative morbidity during the first postoperative week

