11.2. Clinical investigation assessments

Patients that are scheduled for vitrectomy surgery that is commonly performed either 23G or 27G instruments will be included. The preoperative preparation of the patient and the surgery itself will not be different from the standard of care. In the postoperative period, some additional examinations will be performed on the first postoperative day:

• The patient will be asked to grade the amount of postoperative pain experienced (using a pain scale as below)

- A photograph will be taken from the outside eye, and the amount of reddishness will be graded by and independent observer. See annex A. Photos to be made without flash, with eyes looking in all directions (e.g. 4 directions with lid up and down) and distance chosen such to have the eyes on photo with subjects not recognizable.
- A questionnaire will be given to the patient upon discharge from the hospital with questions to assess the postoperative recovery. The patient will be asked to mail us these questions back after one week.
- 1. Are you self-employed / employed/ retired / disabled / other:
- 2. Did you sleep less well during the first night after surgery due to eye pain? Yes / No $\,$
- 3. Did you sleep less well during the first week after surgery due to eye pain? Yes / No
- 4. Did you wake up during the first night due to eye pain? Yes / No
- 5. Did you wake up during the first week due to eye pain? Yes / No
- 6. Did you take pain medication during the first night after surgery due to eye pain? Yes / No
- Did you take pain medication during the first week after surgery due to eye pain? Yes / No
- Did you use an eye cream after the surgery during pain or abrasive feeling? Yes / No

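### The questionnaire's one-week items include the first night, so persistence in patients with first-night symptoms cannot be identified

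*Combined protocol and SAP*

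**What the plan says.** Section 11.2 lists the patient questionnaire. Items are numbered here in order of appearance. Three symptoms are each asked about twice, as Yes/No:

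- Sleep: "Did you sleep less well during the first night after surgery due to eye pain" (item 2) and "Did you sleep less well during the first week after surgery due to eye pain" (item 3).
- Waking: "Did you wake up during the first night due to eye pain" (item 4) and "Did you wake up during the first week due to eye pain" (item 5).
- Pain medication: "Did you take pain medication during the first night after surgery due to eye pain" (item 6) and "Did you take pain medication during the first week after surgery due to eye pain" (item 7).

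Item 8, on eye cream, stands alone and refers only to the time since surgery. The form is handed out at discharge and mailed back once, after a week. There is no daily record.

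Section 11.1 states the purpose of the form: "To be completed by the patient about postoperative morbidity during the first postoperative week". In the flowchart (7.3) the questionnaire is the only row marked at week 1. Visual acuity, pain assessment, intra-ocular pressure, slit lamp and eye photo are marked at day 1 only, and section 11.1 limits the pain scale to the first 24 hours.

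**The concern.** None of items 3, 5 and 7 says that the first night is to be left out, and the first night is part of the first week. A patient troubled on night 1 only, answering literally, must say Yes to both items of the pair. So must a patient whose trouble continued. The two cannot be told apart.

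The objective in section 6.1 is a comparison of postoperative recovery. For that objective it matters whether patients who had symptoms on the first night then improved, and whether they did so differently by gauge. Only this form is scheduled to collect outcome data after day 1, and on that question it is silent. A difference between arms on a week item may simply repeat the first-night difference, while a real difference in persistence may leave no trace.

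**Working it through.** The plan has no figure of its own to reproduce. Section 13.2 sizes the trial on cells, tyndall and redness, and no rates are given for the questionnaire. The check therefore asks what the paired answers can identify. All rates below are assumptions.

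**Answer patterns, literal reading (night item / week item)**

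| Pattern | What it shows |
|---|---|
| No / No | No symptom at any time in the week |
| No / Yes | Symptom began after night 1 |
| Yes / Yes | Night 1 only, or persistence: not separable |
| Yes / No | Logically impossible |

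A Yes/No pair would reveal a patient who took the week item to mean the rest of the week. If some patients read it that way, a Yes/Yes from them means persistence, but it looks the same as a literal Yes/Yes.

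**Formulas.** Let n = P(Yes on the first night), s = P(symptom later in the week, given Yes on night 1), and o = P(symptom later in the week, given No on night 1).

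- Observed: P(week Yes) = n + (1 − n)·o. Persistence s does not appear.
- Wanted: P(symptom after night 1) = n·s + (1 − n)·o.
- With s anywhere from 0 to 1, the wanted rate lies between (1 − n)·o and n + (1 − n)·o, an interval of width n.

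| n | Bounds, o = 0 | Bounds, o = 10% |
|---|---|---|
| 10% | 0 to 10% | 9 to 19% |
| 30% | 0 to 30% | 7 to 37% |
| 50% | 0 to 50% | 5 to 55% |

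**A real difference that disappears.** Take n = 40% and o = 10% in both arms, with s = 20% in one and 80% in the other.

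- Week item, both arms: 0.40 + 0.60 × 0.10 = 46%.
- No/Yes, both arms: 0.60 × 0.10 = 6%.
- True rate after night 1: 0.40 × 0.20 + 0.06 = 14% against 0.40 × 0.80 + 0.06 = 38%.

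Every observable proportion is the same in the two arms, although the true later rates differ by 24 points.

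**A first-night difference that carries over.** Take n = 20% against 50%, with nothing later (s = o = 0). The week item gives 20% against 50%, while the true rates after night 1 are 0 and 0.

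**What remains visible.** Take n = 40% in both arms, with later onset o = 5% against 30%. The No/Yes pattern gives 0.60 × 0.05 = 3% against 0.60 × 0.30 = 18%. A difference in new onset can be seen.

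**Scale at one site.** With 25 patients per group (section 13.2) and n = 40%, 0.40 × 25 = 10 patients per arm would have an uninformative Yes/Yes pair.

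**The case against.** A reader might infer that the form says nothing about morbidity after the first night. It does not go that far. Both answers come from the same patient, so No/Yes and No/No pairs are informative and can be compared between arms. If later symptoms did not depend on night 1 (s = o within each arm), the patients free of symptoms on night 1 would recover the later rate, with only a loss of precision. This stands, and it limits the point to persistence. It does not remove it: pain on night 1 may well predict pain later, and restricting to patients without first-night symptoms conditions on an outcome that arises after randomisation. Section 13 plans no analysis of the paired patterns.

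A second stronger reading is that a conclusion on speed of recovery must come out wrong. No section plans such a statement. A cumulative week item does measure morbidity over the first week, which is the purpose section 11.1 gives. It misleads only if it is read as an effect after the first night.

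Third, the consequence is limited. The primary parameters, redness and intra-ocular inflammation, are assessed on day 1. Safety events are also recorded over the investigation with onset and end dates (19.5), although section 11.4.1 exempts several common transient events from reporting. The questionnaire is therefore the only scheduled outcome assessment after day 1, not the only information of any kind.

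Finally, rewording does not make a single site well powered. For 14% against 38% with 25 per arm at two-sided 5%, the pooled-variance normal approximation gives z = (0.24 − 1.96 × 0.1241)/0.1193 = −0.03, a power of about 49%. This is true, but it concerns sample size; as worded, the form could not show this difference at any sample size.

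**Conclusion.** The point holds in a limited form. On the literal wording, a Yes/Yes pair cannot separate symptoms confined to the first night from persistent ones, so later morbidity is identifiable only in patients free of the symptom on night 1. The rate after night 1 is known only within an interval as wide as the first-night rate.

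Under the assumed rates, a 24-point difference in later morbidity shows as zero on the week item. These rates are illustrative, and the size depends on how common first-night symptoms are and how far persistence differs from new onset. That the week includes the first night is the plain reading, but the form does not state it; mixed readings by patients would add inconsistency. The primary comparison is untouched. This is a worthwhile, inexpensive correction to the plan's only scheduled outcome data after day 1, not a flaw that undermines the trial.

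**What to change.** Reword items 3, 5 and 7 so that each asks about the period after the first night, up to one week after surgery. Derive the whole-week outcome as Yes on either item of the pair, so that nothing now collected is lost. Base any statement on recovery after the first night on the reworded items only.

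Leave item 8 covering the whole week. It has no first-night partner, and a later window would discard eye cream used on night 1.

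The cost is a few words on the form and an ethics notification, with no added visit or procedure. If patients have already returned the old form, their week items cannot be merged directly with the new ones. At best they correspond to the derived whole-week outcome, and only if those patients read the item literally.

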11.3. Surgical procedure

The patient will be operated under local anesthesia, local anesthesia with sedation or general anesthesia, depending on the surgeon's and patient's preferences and general status of health. In the patients is phakic, the surgery may be combined with a cataract surgery (phaco-emulsification). As in the standard of care in each surgical center, the patients may stay overnight in the hospital after the surgery or can be treated on an outpatient basis.

11.4. Safety assessments

Medical device incidents will be routinely collected and reported under the national rules at the discretion of the Investigator.

11.4.1 Adverse events that do not require reporting

After vitrectomy, the following transient adverse events are commonly present during the first week after surgery, hence will not require reporting:

- Decreased visual acuity compared to preoperative measurement
- Reddish eye
- Increased ocular pressure
- Mild to moderate intra-ocular inflammation
- Mild corneal edema

12. DATA QUALITY ASSURANCE

12.1. Monitoring, Audit and Inspections

Investigator and the institution(s) will permit trial-related monitoring, audits, EC review, and regulatory inspections (where appropriate) by providing direct access to source data and other documents.

12.2. Training of staff

The Principal Investigator will ensure that appropriate training relevant to the investigation is given to the medical, nursing and other staff at the site involved and that new information of relevance to the performance of this investigation is forwarded to the staff involved.

The staff at the investigational site will sign a confirmation document that they are trained.

12.3. Data Management

In this study, an electronic case report form (eCRF) within the RedCap platform will be used for data capture. For each surgical center, a different RedCap database will we created, allowing only access to the corresponding investigator and CRO (in case assigned by the CTC). Hence, there will be no sharing of data between the different surgical centers. Also, the data of the different centers will not be pooled for comparison between the centers, only comparison within each center will be performed (see section statistical analysis). Hence, during the whole trial there will be a strict separation of study data between each center.

All documents will be stored safely in confidential conditions. On all clinical investigationspecific documents, other than the signed consent, the participant will be referred to by the clinical investigation participant number/code, not by name.

All clinical investigation documentation will be kept for 10 years from the clinical investigation plan defined end of clinical investigation point. When the minimum retention period has elapsed, clinical investigation documentation will not be destroyed without permission from the sponsor.

13. STATISTICS

General comment: for the statistical analysis, a comparison will be made between both study arms included *in each center*. Hence, there will only be a comparison between both study arms in each site. No pooling of the data from the different sites will be performed nor will there be a comparison between the different study sites.

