13.1. Description of statistical methods

Missing data handling

The missing processes was described by Rubin (1987) who made a distinction between (a) Missing Completely At Random (MCAR), (b) Missing At Random (MAR), and (c) Missing Not At Random (MNAR)¹. We will test with the statistical test of Jamshidian and Jalal (2010), implemented in the MissMech R Package (Jamshidian et al., 2014), whether missing data were MCAR. If they are not MCAR, we will investigate whether or not the missing mechanism could be explained by baseline characteristics (eg, sociodemographic, medical features) of patients using logistic regression, which would suggest an MAR mechanism. If missing data are not MCAR or MAR, they will considered as MNAR. As indicated by Molenberghs et al. (2008) one can never totally exclude a MNAR process, but every MNAR model has an MAR counterpart with equal fit. Therefore, in case of MCAR, MAR, or MNAR missing processes, maximum likelihood (ML) and multiple imputation (MI) were used, using the mice R package for the last one (Raghunathan et al. (2001) ; van Buuren & Oudshoorn (2016)) with a predefined seed. Indeed, ML and MI use all available data in the study and produce unbiased estimates of the treatment effect and correct P values. MI is also a method of choice because it allows not only to impute missing values on the outcome but also on the covariate (Dziura, 2013) and is valid for MCAR, MAR, and MNAR. (Molenberghs et al. (2008)) Molenberghs and Kenward (2007) recommended ML estimation without imposing a structure on the covariances among the repeated measures.

Analysis of primary outcomes

The primary outcomes will be analysed by a set of Wilcoxon-Mann-Whitney tests, but complementary tests will be done using mixed models for ordinal data (Hedeker & Gibbons, 2006) to take the multicenter nature of this trial into account. It is likely that patients in the same centre will tend to have correlated outcomes, meaning that they are more similar to other patients recruited within the same centre that to patients: same clinical care paths within centres will be observed, medical centre having their own medical practice preferences, and, therefore, the independence assumption underlying classical statistical tests is likely to be violated. We will therefore take this correlation between the patients of a same centre into account by using mixed models with the centre included as random effect for continuous outcomes (Chu et al., 2001; Kahan &

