¹ (a) Missing Completely At Random (MCAR): the missingness pattern is independent from observed and unobserved data; (b) Missing At Random (MAR): conditional on the observed data, the dropout is independent of the unobserved measurement; and (c) Missing Not At Random (MNAR): when neither MCAR nor MAR hold, the missingness depends on the observed, as well as on the unobserved data.

Morris, 2013) and mixed models for discrete data will be used to model binary outcomes (Kahan & Harhay, 2015).

For demographic and baseline data, continuous data will be compared by means of T-test when homogeneity of variances, tested with the Bartlett's test, and normality of the residuals, tested with the Shapiro-Wilks test, will be reached and means and standard deviations (means \pm StDev) will be reported. When homogeneity of the variance or normality of the residuals won't be proved, Wilcoxon signed rank test will be performed on rank data and medians and inter-quartile ranges (median [Q₂₅ - Q₇₅]) will reported. For count data, the Pearson Chi-Squared test will be performed to compare proportions. We will use the software R, version 3.6.2 or above (R Core Team, 2017) to perform the statistical analyses.

Hedeker D, Gibbons RD (2006). Longitudinal Data Analysis. Wiley-Interscience, Hoboken, NJ.

Kahan, B.C. & Haray, M.O. (2015). Many multicentre trials had few events per centre, requiring analysis via random-effects models or GEEs. Journal of Clinical Epidemiology, 68(12), 1504-1511.

Kahan, B.C. & Morris, T.P. (2013). Analysis of multicentre trials with continuous outcomes: when and how should we account for centre effects? Statistics in Medicine, 32(7), 1136-1149.

Rubin DB. Inference and missing data. *Biometrika*.1976;63:581–592.

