13.2. The number of participants

We estimated the number of participants by calculating the number of participants needed for the three chosen outcomes (bio cellen, bio tyndall and redness of the eye), based on the pilot data. The target p-value was 0.5/3 (=0.0167) in order to correct for multiple testing, and the power was set to 80%. Because we want to see a difference on the three outcomes, we choose the highest sample size estimation, based on the work of Zaho, Rahardja & Yongming (2008), who proposed sample size estimators ordinal data using the Wilcoxon-Mann-Whitney test and available in the R package *sample size*. The percentages for each categories of the ordinal variables by group are used as input for the sample size estimations. The next table presents the results obtained.

	Total by group	Total individuals
Bio cellen	428	858
Bio tyndall	430	860
Redness eye	27	54

Based on this table, a total of 860 patients would be required by group in order to show a difference between 23G and 27G on the three parameters of the outcome: bio tyndall, bio cellen and redness eye.

For each surgical site 25 patients will be recruited by group (i.e. 50 patients will be included at each site).

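### Section 13 allows only within-site arm comparisons and bars pooling, yet section 13.1 plans mixed models across centres, and no rule turns the site results into one answer

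*Combined protocol and SAP*

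**What the plan says.** **Level of the comparison.** Sections 5, 12.3 and 13 all place the comparison of arms inside each centre. The general comment that opens section 13 governs everything under it and adds: "No pooling of the data from the different sites will be performed nor will there be a comparison between the different study sites". Section 12.3 gives every centre its own database. It says that "the data of the different centers will not be pooled for comparison between the centers, only comparison within each center will be performed" and that "during the whole trial there will be a strict separation of study data between each center".

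**Planned models.** Section 13.1 tests the primary outcomes with Wilcoxon-Mann-Whitney tests, without restating the level. It adds that "complementary tests will be done using mixed models for ordinal data" to allow for the multicentre design. It goes on to account for correlation within centres by "using mixed models with the centre included as random effect for continuous outcomes", and says that "mixed models for discrete data will be used to model binary outcomes".

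**Size.** Section 13.2 derives 428 per group for cells, 430 for flare (tyndall) and 27 for redness, at a significance level of 0.0167 and 80% power. It ends with the recruitment target: "For each surgical site 25 patients will be recruited by group (i.e. 50 patients will be included at each site"). Section 8.1 gives 500 patients in total, at most 50 per site.

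**Error rate.** Section 13.3 sets 5% two-sided and promises adjustment that keeps the overall type I error at 5%. Section 13.2 divides only by the three outcomes.

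**Question.** Section 6.1 states a single objective: a randomised comparison of recovery after 27G and after larger-gauge surgery.

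**The concern.** The variance of a centre random effect cannot be estimated from one centre. An analyst who obeys section 13 cannot fit the models in section 13.1, and one who fits them breaks section 13. Calling the models complementary does not help, because the ban has no exception.

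The choice decides what the trial can show. Under the stated rule, each site stands alone with 25 patients per arm, and the text has no step from ten or so sets of site results to an answer to section 6.1. It does not say what a positive result at some sites and not at others would mean. It also leaves open whether the 5% is to be held within a site or over all sites.

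**Working it through.** **1. The passages side by side.** Section 13: arms compared within a site, no pooling. Section 13.1: centre as a random effect, justified by the worry that correlation within centres breaks the independence assumption of classical tests. That worry arises only when patients from several centres are analysed together. The two sections therefore assume different data sets.

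**2. The plan's own figures.** Section 13.2 prints the level as 0.5/3, which is 0.167. The stated 0.0167 is 0.05/3, and that is used here. The table's totals: 2 x 430 = 860 and 2 x 27 = 54 agree; 2 x 428 = 856 against 858 printed, which is consistent with rounding. The sentence below the table calls 860 a per-group number, but the table gives 430 per group, and the table is used here. The sample sizes themselves cannot be reproduced, because the pilot category percentages are not given.

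**3. Back-solved effect.** Take each tabulated n as giving 80% power at two-sided 0.0167. The noncentrality at n per arm is then

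(2.394 + 0.842) x sqrt(n / n_plan),

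and power is about Phi(noncentrality - 2.394), plus a negligible opposite tail.

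**4. One site, n = 25.**
- Flare: 3.236 x sqrt(25/430) = 0.78; power 0.054.
- Cells: 3.236 x sqrt(25/428) = 0.78; power 0.054.
- Redness: 3.236 x sqrt(25/27) = 3.11; power 0.764.

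Section 13.2 wants a difference on all three outcomes. Power for all three at one site cannot exceed the smallest of them, about 5%.

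As a check on the approximation, tied ordinal grades were simulated under four assumed grade distributions. This gave 0.048 to 0.052 for an effect sized at 860 in total and 0.796 to 0.810 for one sized at 54.

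**5. All sites combined, n = 250 (500/2).**
- Flare: 3.236 x sqrt(250/430) = 2.47; power 0.529.
- Cells: 3.236 x sqrt(250/428) = 2.47; power 0.531.
- Redness: above 0.999.

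**6. Error rate over sites.** The fewest sites that can supply 500 patients is 500/50 = 10, so there are 10 x 3 = 30 tests. With 0.0167 per test and no adjustment across sites, the chance of at least one false positive is:
- outcomes within a site fully correlated: 1 - (1 - 0.0167)^10 = 0.155;
- all tests independent: 1 - (1 - 0.0167)^30 = 0.396.

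If the 5% is spread over all 30 tests, each is made at 0.05/30 = 0.00167. Power at one site is then 0.009 for cells and flare and 0.488 for redness.

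**The case against.** The strongest reply is that the plan does state the level. The general comment in section 13 applies to the whole section, sections 5 and 12.3 agree with it, and the mixed models are only complementary. This stands. A reader might infer that the plan never says whether the primary tests are per site or overall, but section 13 says per site. The fault is that section 13.1 contradicts this and that no combination rule follows.

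Other stronger readings also fail:
- **Section 13.2 shows that a combined analysis was intended.** It does not. The 430 per group exceeds both 25 at a site and 250 combined, and redness at 27 per group is close to a site's 25.
- **The single statistician's report in section 17.2 implies pooling.** One report can hold separate site results.
- **Section 12.3 bars only pooling for comparisons between centres.** Its wording is narrower than section 13's, but the same sentence restricts the analysis to comparisons within each centre.
- **No statistician may see data from all sites.** Section 14.1, on the parties involved, is not in the text available for review, so this cannot be concluded.
- **A false-positive chance of 15% to 40% is built into the plan.** It arises only if the adjustment in section 13.3 is not applied across sites. What is missing is a definition of the family of tests.

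Section 13.6 requires a final statistical plan before any analysis. That limits choices made after results are seen. It does not supply the rule now, and a later plan cannot set aside the protocol's ban without an amendment.

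It is also fair to say that much of the low power comes from the sample size, whichever level is chosen.

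**Conclusion.** The plan is wrong as written and must be corrected before analysis. The per-site rule and the cross-centre models exclude each other, and the path from site results to the primary objective is undefined. Following the stated rule leaves two of the three primary outcomes almost untestable at any site (about 5% power, against about 76% for redness). A combined analysis reaches about 53% and above 99%.

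These figures rest on the per-group numbers in the section 13.2 table, two-sided 0.0167, a normal approximation, no dropout, full recruitment of 250 per arm for the combined case, and the same effect whether the comparator is 23G or 25G. The contradiction itself rests on none of these assumptions. The gap between 53% and the planned 80% is a separate sample-size issue, which settling the level of analysis does not close.

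**What to change.** **Sections 12.3, 13 and 13.1.** Limit the ban to comparisons between centres and to sharing of data between sites. Make the primary analysis of each outcome one rank test stratified by centre, for example van Elteren, which compares arms within centres and combines the within-centre results. Other stratified tests would also serve. This keeps the aim in section 5 of judging 27G against each centre's own standard. Keep the ordinal mixed model as supportive.

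**Section 13.3.** Apply the 5% across the three overall tests, 0.05/3 each. Report results by site and by comparator gauge descriptively, with intervals.

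**If patient-level data must stay separate.** Combine a summary statistic and its variance from each site by a stratified rank test or a two-stage meta-analysis. State that this is not barred as pooling, and drop the one-stage mixed model.

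**If only site results are wanted.** Delete the mixed models, state that no overall conclusion will be drawn, give the per-site power, and say whether the 5% applies per site or across sites.

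**Cost.** A protocol amendment with sponsor and ethics committee review (sections 15.3 and 16.1), made before any analysis, and a check that consent covers the chosen data flow. No new visits or measurements are needed. Site p-values would no longer be confirmatory, the overall effect would average over 23G and 25G comparators, and power for cells and flare would still be only about 53%.
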